- 2) To determine whether any benefits of amisulpride are maintained by prolonging treatment beyond 12 weeks. Duration of stage 2 treatment was initially 24 weeks but was then reduced to 12 weeks, to enhance numbers still on treatment at their final assessment.

Secondary objectives

ATLAS will also investigate:

- (i) The associated risks of side-effects and serious adverse events;
- (ii) Compliance with allocated treatment;
- (iii) The effects of treatment on quality of life;
- (iv) The cost-effectiveness of amisulpride treatment.

Trial design

ATLAS is a pragmatic, randomised, 3-arm, double-blind placebo-controlled trial with two stages:

Stage 1 – an initial double-blind placebo-controlled stage to investigate efficacy and tolerability of oral amisulpride (arms A and B) versus placebo (arm C) over 12 weeks.

Stage 2 – a second double-blind stage investigating the effects of treatment continuation (arm A) versus switching to placebo (arm B) over a further 24 (initially, later 12) weeks.

Randomisation (3 Groups)

 Stage 1 – Weeks 1-12	 Stage 2 – Weeks 13-24 (or 36)	
(A) Amisulpride		Amisulpride
(B) Amisulpride		Placebo
(C) Placebo		Amisulpride

Outcome measures

Primary Efficacy Parameter – Brief Psychiatric Rating Scale

The first primary outcome measure is the Brief Psychiatric Rating Scale (BPRS), a widely used clinician-rated instrument for assessing positive, negative and affective symptoms in patients with psychotic disorders. The BPRS consists of 18 symptom constructs. Each item is assessed by the rater on a 7-point scale ranging from 1 (not present) to 7 (extremely severe). The total score is obtained by summing the scores from the 18 items. Scores thus range from 18 to 126, with higher scores indicating greater levels of psychopathy. The BPRS will be administered at baseline, at week 4, then again in weeks 10-12, week 16 and the final assessment (weeks 22-24 or 34-36). Change in BPRS score between baseline and the week 10-12 assessment and between the week 10-12 and final assessments are the trial's co-primary outcomes.

The second primary outcome measure is the proportion of patients withdrawn to open treatment by their physicians because of perceived lack of efficacy.

Secondary Efficacy Parameters

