With 100 patients, allowing for a 10% drop-out rate by 12-weeks, i.e. 90 of 100 with outcome assessments, ATLAS would have 70% power at 2p<0.05 to detect the MRD of 5 points between those taking amisulpride and placebo in stage 1, and ample power to detect larger differences.

4. General considerations

Study population:

Primary analyses of each stage will include all patients who have taken any study treatment in that stage. Participants who withdrew after pack allocation but before receiving any treatment can be safely excluded as treatment allocation is double-blinded so treatment allocation cannot influence the decision to withdraw and so introduce selection bias. Analyses of this population will be by intention to treat (ITT), ie all participants will be analysed in the treatment arm to which they were randomised, whether or not they adhered to the treatment. This is to avoid any potential bias in the analysis. Secondary analysis such as 'per protocol' (only those participants who adhere with the treatment allocation) may be carried out but as a sensitivity analysis only.

P-values:

Unless otherwise specified, estimates of amisulpride efficacy will be presented with 95% confidence intervals. P-values will be from two-sided test. No corrections for multiple testing will be made in the primary analyses.

Missing data:

The primary endpoint will be analysed using repeated measures analyses of all available data, which minimises impact of missing data. If a score is missing for a participant it is just missing. It has no effect on the other scores from the same participant.

Late data:

The week 4 and week 16 assessments should, where possible, be undertaken within ± 7 days of the scheduled date. The other assessments (e.g. 10-12 week and 22-24 week) allow a ± 14 day leeway. As deviations from scheduled assessments are possible in a study of participants with very late-onset schizophrenia-like psychosis assessments outside these windows will be included as if at the specified time point with no specified time limit.

Timing of interim analyses:

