The main analysis will be undertaken once all patients have reached 22-24 weeks from randomisation. To assess the efficacy of 12 weeks of amisulpride in Stage 1, the primary outcome of BPRS will be compared using repeated measures regression model. Data from week 4 and week 12 will be the outcome variables and baseline scores will be entered into the model as a covariate. Time will be modelled as a categorical variable. The comparison will be between active amisulpride treatment (arms A and B group together) and placebo (arm C). The six minimisation factors (age, gender, home circumstance, BPRS score, time since onset of symptoms and previous antipsychotic treatment) will also be included as covariates in the repeated measures model. A time by treatment interaction parameter will be included to examine if there is any changing treatment effect over time. Treatment effects are presented with 95% confidence interval and associated p-values in each case. For these analyses a p-value of 0.05 (5% level) will be used to indicate statistical significance. This analysis uses all available visit data which will maximise statistical power to detect any difference at visits

To assess the value of continuing treatment in Stage 2, arm A (amisulpride – amisulpride) will be compared with arm B (amisulpride – placebo). Most patients will have only one outcome time point at week 24 or 36; the protocol has now been amended to shorten Stage 2 to 12 weeks with an additional assessment at about week 16. So, an analysis of covariance will be carried out, using the week 12 BPRS as baseline into the model as a covariate. Confidence intervals for the difference in means will be calculated. Participants who withdraw in Stage 1 will not be included in this analysis.

The BPRS covers the important symptoms elicited in very late-onset schizophrenia-like psychosis patients. In particular the Hostility, Suspiciousness, Hallucinations, Unusual Thought Content, Tension, and Uncooperativeness items of the BPRS all assess important areas of psychopathology in

these patients. The 7-point rating of the BPRS on each of these items generates a sub-score for these six symptoms domains that the protocol pre-specified as those most likely to be affected by the disorder. Scores on the subset range from 6 to 42, with higher scores indicating greater levels of psychopathology. The sub-score will be analysed in the same way the full BPRS analysis, for both Stage 1 and Stage 2.

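### With no time limit on late visits, a week-12 BPRS taken after the Stage 2 switch can enter both co-primary BPRS analyses as if taken before it

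*SAP*

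**What the plan says.** - **Section 4, Late data.** Weeks 4 and 16 have a window of 7 days either side. "The other assessments (e.g. 10-12 week and 22-24 week) allow a ± 14 day leeway". Beyond the windows, "assessments outside these windows will be included as if at the specified time point with no specified time limit".
- **Section 3, Trial design.** Stage 1 covers weeks 1-12 and Stage 2 starts at week 13. Arm A stays on amisulpride, arm B moves to placebo and arm C moves to amisulpride.
- **Section 3, Outcome measures.** "Change in BPRS score between baseline and the week 10-12 assessment and between the week 10-12 and final assessments are the trial's co-primary outcomes".
- **Section 5.1, Stage 1.** "Data from week 4 and week 12 will be the outcome variables and baseline scores will be entered into the model as a covariate". The visit is fitted as a category, so the actual date of an assessment does not enter the model.
- **Section 5.1, Stage 2.** Arms A and B are compared by analysis of covariance, "using the week 12 BPRS as baseline into the model as a covariate".
- **Section 5.3.** The sensitivity analyses are week 4 carried forward and a restriction to adherers. None is restricted to assessments made on time or before the switch.

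**The concern.** In an ordinary parallel-group trial a late visit mainly blurs timing, because the patient is still on the randomised treatment. Here the randomised treatment itself changes at the visit boundary in two of the three arms. A late arm C score may be a score on amisulpride that is analysed as placebo. A late arm B score may be a score on placebo that is analysed as amisulpride. If the drug works, both errors shrink the Stage 1 difference.

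The same score is the Stage 2 covariate. If it is taken after arm B has switched, it is no longer a baseline: it already reflects some of the A versus B difference, and adjusting for it removes that part from the estimate.

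Analysis by intention to treat does not cover this. That principle keeps patients in their randomised arm despite non-adherence. It does not justify scoring the treatment randomised for one stage as if it were the treatment for the other.

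**Working it through.** **1. Calendar.** The visit is due in weeks 10-12. Adding 14 days to the end of that span gives week 14, after the week 13 start of Stage 2; adding 14 days to week 10 gives only week 12. So an in-window visit can fall after the nominal switch but need not. Beyond the window there is no limit, so a late visit could reach the week 16 window, which opens at week 15.

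**2. The SAP's own power.** Inputs from section 3 (Sample size considerations): difference 5, SD 9, 90 patients assessed, two-sided 5%. The allocation ratio is not stated; three equal arms would give 60 (A+B) versus 30 (C).

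SE = 9 × √(1/60 + 1/30) = 2.012. Power = Φ(5/2.012 − 1.96) = Φ(0.525) = 0.700.

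This reproduces the stated 70%. A 1:1 split of 90 would give 75%, so 2:1 is the ratio that fits.

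**3. Stage 1, arm C scores only.** Two assumptions are needed that the SAP does not supply: p, the share of arm C week-12 scores taken after the switch, and r, the fraction of the drug effect gained by then. Contrast = 5 × (1 − p·r).

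| p | r | Contrast | Power |
|---|---|---|---|
| 0 | – | 5.00 | 70% |
| 10% | 0.5 | 4.75 | 66% |
| 10% | 1 | 4.50 | 61% |
| 20% | 0.5 | 4.50 | 61% |
| 20% | 1 | 4.00 | 51% |

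**4. Stage 1, arm B affected too.** Suppose a share f of scores is late in all arms and arm B loses the fraction r of the effect. Arm C moves by 5fr and the A+B mean by half of 5fr, so contrast = 5 − 7.5fr.

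| f | r | Contrast | Power |
|---|---|---|---|
| 5% | 0.5 | 4.81 | 67% |
| 10% | 0.5 | 4.63 | 63% |
| 20% | 0.5 | 4.25 | 56% |
| 20% | 1 | 3.50 | 41% |

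**5. Stage 2.** Assume a true A versus B difference of 5 and a covariate slope b of 0.5 to 0.7. A share f of arm B baselines is worse by 5r, so the adjusted difference = 5 − b·5·r·f. At f = 20%, r = 0.5 this is 4.75 (b = 0.5) or 4.65 (b = 0.7). At f = 20%, r = 1 it is 4.50 or 4.30. The loss is smaller than in Stage 1.

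All of this compares two means at one time point. The planned Stage 1 model also uses week 4 and adjusts for baseline, so the figures show direction and rough scale only.

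**The case against.** The strongest objection is that the mechanism depends on something the SAP does not show. If Stage 2 medication is issued only once the week 10-12 assessment is done, a late visit simply delays the switch and no score is contaminated. The week 13 start appears in a design schematic, not in a dispensing rule, and dispensing is commonly left to the protocol. This stands, and it limits the point to what can happen. A reader might infer that both co-primary BPRS contrasts are biased; the SAP does not support that.

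A reader might also take the power figures as a forecast. They are not: the shares of 10-20% and the half-to-full effect have no source in the SAP. Within the stated window arm C would have had at most about two weeks of active drug, so a full effect implies much later visits.

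It is also fair to say that the bias is toward no difference, so it would not create a false claim of benefit. That lowers the severity but does not remove the problem in a trial planned at 70% power.

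What the objection does not answer is that the unlimited rule is written down. It is a stated choice, not an omission, and nothing in the SAP bounds its effect or checks for it.

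**Conclusion.** The point holds in conditional form. Unless the Stage 2 switch always waits for the week 10-12 assessment, the late-data rule allows a post-switch BPRS to serve as a Stage 1 outcome under the wrong treatment and as a Stage 2 covariate already affected by the comparison. If amisulpride works, both contrasts move toward zero.

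The size cannot be determined from the SAP. The arm C illustration runs from 4.75 points and 66% power to 4.0 points and 51%, resting on an inferred 2:1 split, a true effect of 5, SD 9, and assumed lateness and speed of effect. The stated 70% is itself correct and is not in dispute. I would rate this as something that should be fixed, with moderate confidence.

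**What to change.** **Change, before unblinding:**
- In the primary analysis, count a BPRS as week 10-12 only if it is dated on or before the patient's first Stage 2 dose. For patients who never start Stage 2 drug, set a fixed calendar limit; the existing 14-day leeway is one candidate.
- In Stage 1, set any other week-12 score to missing. Week 4 still contributes through the repeated measures model.
- In the Stage 2 analysis of covariance, a missing covariate would drop the patient. Keep such patients by imputing the week-12 baseline from pre-switch scores (baseline and week 4), without using arm. A and B were both allocated amisulpride up to the switch, so arm has no place in that imputation.
- Report the as-if-on-time analysis as a sensitivity analysis.
- If the final visit is also given a limit, do not tie it to when a patient actually stops medication. That would exclude early discontinuers and conflict with the intention-to-treat rule in section 4.
- State how the week 10-12 assessment relates to the start of Stage 2, or refer to where this is set out.

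**Cost:** SAP wording, a check of assessment dates against first Stage 2 dose dates, and some loss of precision. In the same two-mean approximation, losing 20% of scores in every arm (48 versus 24) gives SE = 9 × √(1/48 + 1/24) = 2.25 and power Φ(5/2.25 − 1.96) = 60%. Under the present rule the figure is 56% at half effect and 41% at full effect. With a quarter of the effect gained the present rule gives 63%, so the change is made to remove bias, not to gain power. If the switch does always follow the assessment, the first-dose condition excludes no scores and costs a sentence.

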(i) Extrapyramidal side effects (EPSE) measured with the Simpson-Angus Scale (SAS). The modified SAS used in ATLAS measures nine extrapyramidal signs: gait, arm dropping, shoulder shaking, elbow rigidity, wrist rigidity, leg pendulousness, glabellar tap, tremor and salivation, all of which are assessed by direct examination. Each item is rated on a scale of 0-4, with higher scores indicating greater severity of EPSE. The scale range of the modified SAS is thus 0-36. The SAS has been widely used to measure EPSE within clinical trials and will be administered at baseline, then again at week 4, weeks 10-12, week 16 and weeks 22-24 (initially 34-36). The change in SAS between baseline and week 10-12 and between week 10-12 and the final assessment (week 22-24 or 34-36) will be compared between groups to assess EPSE.

(ii) **Compliance** expressed as treatment discontinuation rates and as percentage of prescribed trial medication taken between weeks 1 and 10-12 and between weeks 13 and the final assessment will be compared in patient allocated to receive amisulpride and those allocated placebo.

(iii) Quality of life measured with the self-rated, 26-item, WHO Quality of Life Scale (WHOQOL-BREF) at baseline, 10-12 weeks and the final assessment. The WHOQOL-BREF includes two items about an individual's overall perception of their quality of life and health and questions assessing four

domains; physical, psychological, social and environmental well-being, which higher scores denoting a better quality of life.

A separate analysis plan for the cost-effectiveness will be drafted.

Sample size considerations

Because of the likely problems with recruitment and retention of patients with late-onset, schizophrenia-like psychosis, ATLAS included an initial Feasibility Phase following which, a pragmatic decision was made to reduce the target sample size from 200-300 to at least 100 participants, to be recruited by mid-2016. The statistical power calculations have been amended with the main emphasis being to answer the primary stage 1 question of whether 12 weeks of amisulpride provides worthwhile benefit. The minimal clinically relevant difference (MRD), given the potential hazards of antipsychotic drugs, is considered to be 5 points on the BPRS. We estimate that the standard deviation of BPRS scores will be 9 points. We are thus powering the trial on a minimal worthwhile standardised effect size of 0.56 (=5/9) standard deviations, a moderate treatment effect.

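### The Stage 1 model lists no baseline-BPRS-by-time term; if the baseline slope weakens by week 12, the week 10-12 contrast loses precision or is reported with too wide a standard error

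*SAP*

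**What the plan says.** SAP section 5.1 specifies the Stage 1 model thus: "Data from week 4 and week 12 will be the outcome variables and baseline scores will be entered into the model as a covariate". The time term is categorical, the six minimisation factors (BPRS score among them) are further covariates, and one interaction is named: "A time by treatment interaction parameter will be included to examine if there is any changing treatment effect over time". No baseline-by-time term is listed. The section does not exclude one either, names no covariance structure, and does not say whether the week 12 contrast or an average over visits is the primary estimate. It justifies the model on the ground that using every visit maximises power.

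Section 3 (Outcome measures) points to the later visit, since the Stage 1 co-primary is "Change in BPRS score between baseline and the week 10-12 assessment".

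The sample size text in section 3 gives the design figures. The smallest worthwhile difference "is considered to be 5 points on the BPRS". On spread: "We estimate that the standard deviation of BPRS scores will be 9 points". The result is that "ATLAS would have 70% power at 2p<0.05 to detect the MRD of 5 points". No correlation between visits is given anywhere.

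**The concern.** A programmer following section 5.1 literally would fit one baseline coefficient to both visits. If baseline BPRS predicts the week 4 score more strongly than the week 12 score, the fitted coefficient lies between the two true slopes and nearer to week 4, the visit with the smaller residual variance. The week 12 scores are then adjusted with too steep a slope, and the surplus goes into the week 12 residual variance.

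With complete data and visit-specific slopes, the week 12 effect is the one a plain week 12 analysis of covariance would give (leaving the other covariates aside). With a shared slope the joint model can do worse than that simpler analysis, which runs against the SAP's reason for choosing it. At 70% planned power there is little to spare at this visit.

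**Working it through.** **Inputs from the SAP.** Difference 5, SD 9, two-sided 0.05, 90 of 100 assessed (section 3); arms A and B together against C (section 5.1). The allocation ratio is not stated. Three equal arms are assumed, giving 60 v 30.

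**Reproducing the stated power.** SE = 9 × √(1/60 + 1/30) = 9 × √0.05 = 2.012. Power = Φ(5/2.012 − 1.96) = Φ(0.524) = 70.0%. The figure reproduces. It is an unadjusted comparison of two means, so the baseline term does not enter it.

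**Assumptions for the comparison.** Correlations r4 (baseline-week 4), r12 (baseline-week 12) and r (week 4-week 12) are not in the SAP and are varied. SD is 9 at every visit and the residual covariance is unstructured.

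**Formulas** (variances in units of 9²; with equal SDs the slopes equal the correlations).
- Residual terms given baseline: v4 = 1 − r4², v12 = 1 − r12², c = r − r4·r12.
- Weight on week 4 in the shared slope: w = (v12 − c)/(v4 + v12 − 2c).
- Shared slope: bc = w·r4 + (1 − w)·r12.
- Week 12 residual variance: v12 with visit-specific slopes; v12 + (r12 − bc)² with the shared slope.
- SE = 9 × √(residual variance × 0.05); power = Φ(5/SE − 1.96).

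**Worked case (0.7, 0.4, 0.6).** v4 = 0.51, v12 = 0.84, c = 0.60 − 0.28 = 0.32. w = 0.52/0.71 = 0.732. bc = 0.732 × 0.7 + 0.268 × 0.4 = 0.62, against a week 12 slope of 0.40. Added variance = 0.22²/0.84, about 5.7%. SE is 1.844 with visit-specific slopes and 1.897 with the shared slope; power is 77.4% and 75.1%.

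| r4, r12, r (assumed) | Fall | Added variance | SE: visit-specific / shared | Power: visit-specific / shared |
|---|---|---|---|---|
| 0.5, 0.5, 0.6 | 0 | 0% | 1.743 / 1.743 | 81.8% / 81.8% |
| 0.6, 0.5, 0.6 | 0.1 | 0.4% | 1.743 / 1.747 | 81.8% / 81.7% |
| 0.6, 0.4, 0.6 | 0.2 | 1.9% | 1.844 / 1.862 | 77.4% / 76.6% |
| 0.7, 0.5, 0.7 | 0.2 | 2.7% | 1.743 / 1.766 | 81.8% / 80.8% |
| 0.6, 0.3, 0.6 | 0.3 | 4.7% | 1.920 / 1.964 | 74.0% / 72.1% |
| 0.7, 0.4, 0.6 | 0.3 | 5.7% | 1.844 / 1.897 | 77.4% / 75.1% |
| 0.7, 0.3, 0.6 | 0.4 | 11.6% | 1.920 / 2.028 | 74.0% / 69.3% |
| 0.8, 0.3, 0.5 | 0.5 | 20.6% | 1.920 / 2.109 | 74.0% / 66.0% |

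In the last two rows the shared-slope SE exceeds the unadjusted 2.012, so adjusting with that slope is worse than not adjusting.

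**Simulation check, including balance.** 100 patients, 2:1, 10% of week 12 missing, 2,000 runs per setting, true effect −5. Mean week 12 estimates from the two models agreed to within 0.03 in every setting. With allocation balanced on baseline BPRS:
- (0.6, 0.4, 0.6): true SD of the estimate 1.832 shared, 1.822 visit-specific; model SE 1.838 and 1.819; power 77.0% and 77.9%.
- (0.7, 0.3, 0.6): true SD 1.890 and 1.854; model SE 2.008 and 1.889; power 71.0% and 75.4%.

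Balance therefore removes most of the real loss of precision, but the reported SE stays inflated and power is still lost.

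**Cost when the term is not needed.** At (0.5, 0.5, 0.6) without balancing, model SE was 1.728 shared and 1.732 with the extra term; power 79.9% and 80.0%.

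**The case against.** The strongest reply is that the premise is not in the document. The SAP gives one SD and no correlations, and nothing in it shows that the baseline slope falls between week 4 and week 12. With equal slopes the loss is zero. The slope also depends on the SDs: if scores spread out after baseline, a falling correlation need not mean an equally falling slope. With assumed SDs of 7, 8 and 10 at baseline, week 4 and week 12, the added variance is 0.5% at (0.6, 0.4, 0.6), 2.4% at (0.7, 0.4, 0.6) and 12% at (0.8, 0.3, 0.5). All of this stands, and the point can only be conditional.

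Minimisation on BPRS band (section 5.4: 30-39, 40-49, 50+) also limits the chance imbalance through which a wrong slope raises sampling variance. That is right for the estimate's true variability. It does not repair the reported standard error.

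A main-effect baseline covariate is a legitimate pre-specified choice, and section 5.1 omits the interaction without ruling it out. That too is fair: this is an efficiency improvement and no stated figure is in error.

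Some stronger readings are not supported:
- A reader might infer bias. Randomisation protects the week 12 estimate, and the simulations showed none.
- A reader might infer that the 70% power is overstated. It reproduces as an unadjusted calculation.
- A reader might infer that drop-out linked to the week 4 score enlarges the loss. In simulations with about 12% of week 12 scores missing on that basis (66 v 34, 1,500 trials per setting), the variance ratio moved from 1.018 to 1.030, from 1.074 to 1.051 and from 1.135 to 1.247 at the same three sets of correlations, with SD 9 throughout. The direction is not consistent.

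**Conclusion.** The point holds in conditional form. As written, one baseline slope serves both visits. If that slope weakens by week 12, the co-primary contrast is less precise than it could be or, where baseline BPRS is balanced, has confidence intervals that are too wide. For modest decay the effect is negligible; it reaches several power points only for a fall of 0.4 or more in the correlation, which is a steep assumption.

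These sizes rest on assumed correlations, SD 9 at each visit, a 2:1 split, unstructured covariance, and the week 12 contrast being the primary estimate. Section 3 implies that last condition, but section 5.1 does not fix it. The case for the change is that it costs almost nothing if the slopes are equal and protects a 70%-power comparison if they are not.

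**What to change.** Add a baseline-BPRS-by-time interaction to the Stage 1 repeated measures model in section 5.1, so that each visit has its own baseline slope. Do the same for the six-item sub-score, with its own baseline value. Keep the six minimisation factors as pre-specified; this change gives no reason to drop the BPRS band.

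The cost is one sentence in the SAP and about one degree of freedom. No new data are needed.

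### The Stage 2 co-primary is analysed by a single-outcome ANCOVA with no role for the week 16 BPRS, against the SAP's own rule of repeated measures on all available data

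*SAP*

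**What the plan says.** Section 3 (Outcome measures) makes two BPRS changes co-primary; the second is the change "between the week 10-12 and final assessments". After baseline and week 4, the BPRS is scheduled "then again in weeks 10-12, week 16 and the final assessment (weeks 22-24 or 34-36".

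Section 4 sets two general rules, neither limited to Stage 1:
- Missing data: "The primary endpoint will be analysed using repeated measures analyses of all available data, which minimises impact of missing data".
- Study population: "Primary analyses of each stage will include all patients who have taken any study treatment in that stage".

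Section 5.1 follows the first rule for Stage 1: "Data from week 4 and week 12 will be the outcome variables and baseline scores will be entered into the model as a covariate". For Stage 2 it departs from it: "So, an analysis of covariance will be carried out, using the week 12 BPRS as baseline into the model as a covariate". The reason given is "Most patients will have only one outcome time point at week 24 or 36", although the same sentence records that the amended protocol has "an additional assessment at about week 16". The only exclusion named is of participants who withdrew in Stage 1. Section 5.3 plans a carry-forward analysis for a missing week 12 score and nothing equivalent for Stage 2.

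**The concern.** The two sections prescribe different methods for a co-primary outcome, and the difference affects who is analysed. A single-outcome ANCOVA needs a final BPRS. A patient who was treated in Stage 2 and seen at week 16, but has no final score, contributes nothing, although section 4 would include that patient and use that score.

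The stated reason does not settle the matter. A repeated measures model accepts patients with one outcome visit alongside patients with two, so a majority with one visit is no obstacle.

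Stage 2 asks whether continuing amisulpride is better than switching to placebo, which is primary objective 2. If patients who worsen after the switch are more likely to lack a final score, those left in arm B look better than the whole arm, and A versus B shrinks toward no benefit of continuing. The SAP expects attrition: section 3 says Stage 2 was shortened to raise the number still on treatment at the end.

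**Working it through.** **The SAP's only power figure.** Inputs from section 3 (Sample size considerations): difference 5, SD 9, 90 assessed, two-sided 5%. With 30 versus 60 patients (arm C versus A+B, assuming 1:1:1 allocation, which the SAP does not state):

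power = Φ[(5/9)/√(1/30 + 1/60) − 1.96] = Φ(2.48 − 1.96) = 0.70.

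The stated 70% for Stage 1 reproduces. None is given for Stage 2.

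**Scale of Stage 2.** The same assumptions leave at most about 30 per arm. Power = Φ[(5/s)·√(n/2) − 1.96], with s = 9, or s = 9·√(1 − 0.5²) = 7.79 if the week 12 score correlates 0.5 (assumed) with the final score.

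| Per arm | No covariate gain | Correlation 0.5 |
|---|---|---|
| 30 | 0.58 | 0.70 |
| 25 | 0.50 | 0.62 |
| 20 | 0.42 | 0.53 |
| 15 | 0.33 | 0.42 |

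A 3.5-point difference at 30 per arm would have 0.32 and 0.41. Since the planned ANCOVA adjusts for week 12, the right-hand column is the fairer one if that correlation is about right.

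**Possible bias of the final-visit ANCOVA.** The SAP gives no Stage 2 dropout rate or visit correlations, so everything below except the 5 points and SD 9 is assumed. These are large-sample simulations with a true final difference of 5, in which loss of the final score depends on the change from week 12 to week 16.

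| Assumed loss of final score | Lost, A / B | ANCOVA estimate |
|---|---|---|
| Weakly related to worsening | about 19% / 21-23% | 4.9-5.0 |
| Moderately | 20-22% / 25-30% | 4.7-4.9 |
| Strongly | 25-27% / 34-42% | 4.2-4.7 |
| Most extreme graded case | 30% / 50% | 3.7 |
| All with a rise above 8 points | 16% / 31% | 3.8 |
| All with a rise above 5 points | 27% / 45% | 3.5 |

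The graded rows use several correlation patterns and week 16 effects of 3 or 5. The last two rows use correlations 0.6 (week 12-16), 0.8 (week 16-final) and 0.5 (week 12-final), with a week 16 effect of 4. With all correlations 0.6 and a week 16 effect of 2.5, the same two cut-offs give 4.5-4.8. Shrinkage therefore runs from near zero to (5 − 3.5)/5 = 30%.

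**What week 16 recovers.** If everyone had a week 16 score and loss depended only on observed scores, a likelihood analysis using it would return about 5.0 throughout. But section 5.1 says most patients have only one outcome point, so coverage is below half. Repeating the two cut-off rules with 20-30% coverage (an assumed range):

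| Setting | ANCOVA | With week 16 |
|---|---|---|
| Rise above 5 | 3.4-3.5 | 3.7-3.9 |
| Rise above 8 | 3.7-3.8 | 4.0-4.2 |
| Milder setting (correlations 0.6, effect 2.5) | 4.5-4.8 | about 0.1 higher |

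The gain is about 0.1 to 0.5 points. For a patient with neither a week 16 nor a final score, worsening is unrecorded and no model of the observed scores can restore it.

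**The case against.** The SAP gives a reason for the ANCOVA, and that reason limits what can be gained: with week 16 available for a minority, the more elaborate model still leaves most of any bias in place. This stands, and it is why a sensitivity analysis is needed as well as a new model.

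A reader might infer that the plan drops patients who worsen and move to open treatment. The SAP does not say so. Section 4 keeps patients in their randomised arm whether or not they adhered, so anyone who attends the final visit is analysed. Only those with no final BPRS are lost, and final-visit-only is itself implied by the endpoint definition and the one-time-point sentence rather than stated outright. Withdrawal to open treatment for perceived lack of efficacy is also counted separately as the second primary outcome. The direction of bias is not fixed either: loss from arm A for side effects would act differently.

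Two further readings are tempting. One is that omitting the minimisation factors in Stage 2 is an error; section 5.1 requires them only for the Stage 1 model, and adding them all is a trade-off in about 60 patients. The other is that pooling the 12- and 24-week Stage 2 final visits confounds A versus B; length was set by protocol amendment, not by arm.

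What survives is the mismatch between sections 4 and 5.1, the absence of any role for week 16, and the gap in section 5.3.

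**Conclusion.** The point holds as an inconsistency on a co-primary outcome with a cheap remedy. Section 4 requires all available data by repeated measures; section 5.1 gives Stage 2 a single-outcome ANCOVA, and the reason offered does not rule out the required method.

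The consequence is conditional. If missing final scores follow worsening, A versus B is pulled toward no benefit, by anything from almost nothing to about 30% of 5 points. That range rests on assumed dropout and correlations, and the large losses at its upper end (such as 27% / 45%) appear nowhere in the SAP. Using week 16 would not restore the full difference here; at 20-30% coverage it moves the estimate by about 0.1 to 0.5 points. This should be fixed, but it does not by itself invalidate the Stage 2 comparison.

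**What to change.** In section 5.1, make the Stage 2 primary analysis a repeated measures model with:
- outcomes: week 16 and final BPRS;
- terms: arm, categorical time, arm-by-time, week 12 BPRS and week 12 BPRS-by-time;
- test: A versus B at the final visit.

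Keep the final-visit ANCOVA as a sensitivity analysis. In section 5.3, add a Stage 2 missing-data sensitivity analysis that also covers patients with neither a week 16 nor a final score. The minimisation factors and a term for Stage 2 length are optional. If the ANCOVA is nevertheless retained as primary, section 4 should say that its repeated measures rule covers Stage 1 only, and the Stage 2 sensitivity analysis is still needed. Settle this before unblinded Stage 2 results are seen.

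The cost is SAP wording; the scores are already scheduled. The model has six fixed effects (intercept, arm, time, arm-by-time, week 12, week 12-by-time) against three in the ANCOVA, plus a two-visit covariance, in at most about 60 patients. The gain is partial because few patients have week 16.
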